### 4.1.1 Inclusion Criteria

Each patient must meet all of the following criteria to be enrolled in this study:

1. Has informed consent form (ICF) signed according to local rules and approved regulations.
2. Is aged 18 to 85 years, inclusive.
3. Is admitted to the ICU or intermediate care unit.
4. Has diagnosis of sepsis (<96 hours prior to first study drug administration or < 72 hours prior to AKI diagnosis), according to criteria defined by the American College of Chest Physicians/Society of Critical Care Medicine (Bone 1992)], based on:
  - a. Has a proven or strongly suspected bacterial infection and
  - b. Have at least 2 of the following 4 SIRS criteria within a timeframe of 72 hours at time of AKI diagnosis. Note: it is not required that symptoms are present simultaneously at study randomization:
    - i. Has a core temperature > 38°C or < 36°C.
    - ii. Has a heart rate > 90 beats/minute (unless the patient has a medical condition known to increase heart rate or is receiving treatment to prevent tachycardia).
    - iii. Has a respiratory rate > 20 breaths/minute, PaCO2 < 32 mm Hg or the use of mechanical ventilation for an acute respiratory process.
    - iv. Has a white cell count > 12 000/mm^3 or < 4000/mm^3 or a differential count showing > 10% immature neutrophils (band cells).
5. Has first diagnosis of AKI, defined as any of the following:

AKI Stage 1 or greater, according to the following Acute Kidney Injury Network (AKIN) criteria (Note: adjusted in regards to time-window):

- a. Increase (absolute) in serum creatinine > 26.2 µmol/L (0.30 mg/dL) compared with a serum creatinine value within the previous 48 hours, or presumed to have occurred in the previous 48 hours when compared to a reference\* creatinine value

- b. Increase (relative) in serum creatinine to  $> 150\%$  ( $> 1.5$ -fold) compared with a serum creatinine value in the previous 48 hours or presumed to have occurred in the previous 48 hours when compared to a reference\* creatinine value.

\*The reference creatinine value is a serum creatinine value in the following order of preference:

1. Lowest value within 3 months of the hospital admission. If not available:
  2. At hospital admission. If not available:
  3. At ICU or intermediate care unit admission. If not available:
  4. Lowest value between 3 and 12 months prior to hospital admission

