### **7.7.3 Safety Analyses**

The safety summaries will include all 4 treatment groups, comprising all patients in the safety set.

Treatment-emergent adverse events will be tabulated by treatment group. The number and percentage of patients with at least 1 TEAE will be presented along with a breakdown by system organ class and preferred term, with each patient being counted once at each summarization level. This summary will be repeated for treatment-related TEAEs, TEAEs that lead to study drug discontinuation, by relationship to study drug, by intensity, and for treatment-emergent SAEs.

Laboratory test results (for hematology, clinical chemistry, and urinalysis parameters not considered in the efficacy analyses), vital signs data, and ECG data will be presented in tables summarizing absolute values and change from baseline by treatment group, with shift tables included as appropriate. Other safety data will be listed only.

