9.2. Laboratory Evaluations

Laboratory assessments not used for the efficacy analysis will be used for the safety analysis and be performed by the local laboratory. All summaries will be based on the units provided defined in the eCRF, no conversion will be done. Also, the out of normal range data will be presented.

Hematology and clinical chemistry assessments will be summarized according to the visits and will be assessed at Baseline, Day 1, 3, 5, 7, 14, 21 and 28. Shift tables presenting baseline and post-baseline values below, within, above or below the normal range (normal ranges as provided by the local laboratories), and count tables at each visit will be presented for hematology and clinical chemistry tests with numeric values below, within or above the normal range (normal ranges as provided by the local laboratories) by treatment group for patients in the Safety Set. The percentage will be based on the number of patients who have attended the visit.

Only scheduled assessments will be included in the laboratory summaries. In case of repeat values the last assessment will be used for pre-dose visits and the first value for post-dose visits.

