milestone will be patients with at least 7 days of laboratory data or who were randomized but discontinued or died prior to completing 7 days. The following outputs will be produced for these safety reviews:

Table 14.1.1.1.1	Disposition at Interim Analysis All Enrolled Set
Table 14.1.1.6.1	Concomitant Medications at Interim Analysis Safety Set
Table 14.3.1.1.1	Treatment Emergent Adverse Events at Interim Analysis by System Organ Class and Preferred Term Safety Set
Table 14.3.1.1.2*	Serious Treatment Emergent Adverse Events at Interim Analysis by System Organ Class and Preferred Term Safety Set
Table 14.3.1.3.1	Treatment Emergent Adverse Events at Interim Analysis by Relationship to Study Drug Safety Set
Table 14.3.2.1*	Summary of Cause of Death at Interim Analysis by System Organ Class and Preferred Term Safety Set
Table 14.3.5.3.1	Hematology Shift Table by Treatment at Interim Analysis Safety Set
Table 14.3.5.3.2	Laboratory Results: Hematology at Interim Analysis Safety Set
Table 14.3.5.4.1	Clinical Chemistry Shift Table by Treatment at Interim Analysis Safety Set
Table 14.3.5.4.2	Laboratory Results: Clinical Chemistry at Interim Analysis Safety Set
Table 14.3.6.2.1	Change from Baseline in Vital Signs at Interim Analysis Safety Set
Figure 14.3.6.2.1	Time-course plot of Vital Signs at Interim Analysis Safety Set
Table 14.3.7.1.1*	APACHE II Score at Interim Analysis Safety Set
Listing 16.3.1.1.2*	Deaths Safety Set

* Outputs were requested after the first DMC meeting.

References to ‘Interim Analysis’ will be removed from all titles and footnotes when outputs are provided at safety reviews.

Additional electronic reviews of AE listings provided by pharmacovigilance (PVG) will be conducted at planned time points and the DMC can request ad hoc reviews. See [Table 15-2](#) for a full summary of the planned reviews.

12. Changes in the Planned Analysis

As part of the primary efficacy analysis an additional analysis set PP Day 1-7 Part 1 has been added. The protocol states that primary endpoint should be carried out separately for Part 1 and Part 2, however to do this analysis on the PP Set, the PP Day 1-7 Part 1 Set is needed to be defined to obtain the analysis for Part 1 of the study.

The following are changes from the Protocol Amendment v2.0:

Table 12-1 Summary of Changes from Planned Analysis and Reason

Change	Change
List of subgroups (Sections 2.3 and 8)	Microbial Infection added

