1.4 (06DEC2016)	8.1, 8.1.2	Adjudication committee review added for creatinine clearance data
1.4 (06DEC2016)	8.1, 8.1.2	Formula added for time-corrected endogenous creatinine clearance calculation
1.4 (06DEC2016)	8.1.4	Sensitivity analysis added to repeat primary endpoint analysis based on adjudicated Part 1 data. ANOVA analysis excluding any patients that died prior to Day 8 and descriptive statistics on the primary endpoint will be performed for the sensitivity analysis.
1.4 (06DEC2016)	8.2.2.1	Urine volume and urea clearance calculation formulas were added
1.4 (06DEC2016)	8.2.2.1	Details added on RRT-free day calculation method
1.4 (06DEC2016)	8.3	Added anti-drug antibody data as other efficacy endpoint
1.4 (06DEC2016)	8.3	Iohexol substudy details added
1.4 (06DEC2016)	8.1.5	Category for FE Urea added
1.4 (06DEC2016)	9.1.2	Separate summary of TEAEs where relationship to study drug is 'Possible', 'Probable' or 'Definite' removed
1.4 (06DEC2016)	9.2	Laboratory evaluations analyses modified to be based on shift tables as per normal ranges provided by the local laboratory
1.4 (06DEC2016)	11	Amended list of outputs provided for the interim analysis
1.4 (06DEC2016)	11	Added details of outputs provided for the DMC meetings
1.4 (06DEC2016)	Appendices 15.2, 15.3, 15.4	Added appendices of schedule of DMC reviews, weight ranges and pre-calculated corresponding volumes and CKD-EPI formula used for GFR calculation
2.0 (13JAN2017)	3.2	Total time in ICU/Intermediate care and Total time in hospital endpoint analysis based on time to decision of transfer deleted. Also both periods Day 1 to 28 and Day 1 to 90 added.
2.0 (13JAN2017)	4.3.3.1, 4.3.3.2, 4.3.3.2, 4.3.3.4	'Non-adherence to inclusion/exclusion criteria with enrollment of the patient' is used for eligibility criteria.
2.0 (13JAN2017)	8.1.1	Hyperlink for section 8.1.5 added.
2.0 (13JAN2017)	8.2.2.1	'Urine volume' replaced with 'Urine output' and the time course plot updated to be on urine output (ml/hr) and not on volume of urine

Version (date)	Section	Summary of change
2.0 (13JAN2017)	8.2.2.2	Sentence ‘non mechanical analysis’ replaced with ‘non mechanical ventilation’.
2.0 (13JAN2017)	8.3	Day 1-28 and the day1-90 for ICU discharge and hospital discharge used (like section 3.2).
3.0 (25SEP2017)	General	‘Time-corrected’ only used for reference to AUC of Creatinine Clearance. ‘Standardized’ used elsewhere.

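### For 16 safety laboratory tests, SAP 9.2 names only range-category tables in place of the protocol's values and changes from baseline, so the by-arm tables cannot show further worsening past a limit already crossed at baseline

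*SAP*

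**What the plan says.** Protocol 7.7.3 states that laboratory results not used for efficacy "will be presented in tables summarizing absolute values and change from baseline by treatment group, with shift tables included as appropriate". Values and changes are the main summary there, and shift tables are the supplement.

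SAP 9.2 describes two outputs for haematology and clinical chemistry: "Shift tables presenting baseline and post-baseline values below, within, above or below the normal range", and "count tables at each visit will be presented for hematology and clinical chemistry tests with numeric values below, within or above the normal range". It does not name a mean, median or change from baseline. It adds two restrictions. The first is "Only scheduled assessments will be included in the laboratory summaries", with the first value used when a post-dose test is repeated. The second is "All summaries will be based on the units provided defined in the eCRF, no conversion will be done".

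The SAP's change history (Section 13, version 1.4) records the move: "Laboratory evaluations analyses modified to be based on shift tables as per normal ranges provided by the local laboratory". Table 12-1 in Section 12, titled "Summary of Changes from Planned Analysis and Reason", has no entry for it.

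The other safety measurements are treated differently. SAP 9.3 (vital signs) and 9.5 (ECG) keep observed values and changes from baseline, and 9.5 also compares the worst post-baseline ECG result with baseline.

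**The concern.** A three-level scale records only whether a limit has been crossed. It carries no information on how far a value moves beyond a limit that was crossed before treatment began.

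That matters in this population. Patients enter with sepsis and acute kidney injury, so some tests can be expected to be abnormal at baseline. For leukocytes an abnormal value is itself one of the entry markers ("Has a white cell count > 12 000/mm", or a low count). If one arm tended to push already abnormal values further out, the by-arm laboratory tables could look the same in every group. At stake is the between-arm comparison of laboratory safety in the final report and in any DMC safety review still to come.

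**Working it through.** The plan gives no figure to reproduce. The check compares the texts, counts the affected tests and works through the mechanism.

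**1. Which tests are affected**

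- SAP 9.2.1 lists 7 haematology tests: haemoglobin, haematocrit, leukocytes, differential, erythrocytes, thrombocytes and activated partial thromboplastin time.
- SAP 9.2.2 lists 13 chemistry tests. The total is 7 + 13 = 20.
- SAP 8.2.2.3 gives observed values and change from baseline by visit for creatinine, BUN/urea, sodium and CRP. That removes 4 chemistry tests: 13 − 4 = 9.
- Tests with category tables only: 7 + 9 = **16**. The nine chemistry tests are arterial pH, creatine phosphokinase, total protein, albumin, glucose, potassium, chloride, bicarbonate and lactate.
- AST, ALT, GGT, LDH and bilirubin are not in the 9.2.2 list. SAP 8.2.2.2 gives them values and changes.

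**2. The mechanism, without assumptions**

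SAP 9.2.2 sets the arterial pH range at 7.35 to 7.45. Protocol 6.3.9 uses pH below 7.2 as part of one of its criteria for starting renal replacement therapy.

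| Baseline | Post-baseline | Change | Table cell | Shows as a shift? |
|---|---|---|---|---|
| 7.40 | 7.30 | −0.10 | within to below | yes |
| 7.30 | 7.15 | −0.15 | below to below | no |

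The larger fall, which also crosses the protocol's own 7.2 threshold, is the one that the table does not register.

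**3. How much could be hidden (illustration only)**

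The documents give no baseline out-of-range rates, so this step is assumed throughout. Take one limit at 0, baseline b ~ N(m, 1), and follow-up f = m + 0.6(b − m) + 0.8e + 0.5, where e is standard normal. The baseline to follow-up correlation is 0.6 and the mean worsening is 0.5 SD. About 71% of patients then worsen (f > b). The share of those already out of range at baseline (b > 0), who therefore stay in the same cell, is:

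| Out of range at baseline | Worsening patients who stay in the same cell |
|---|---|
| 16% | 10% |
| 50% | 41% |
| 84% | 80% |
| 98% | 97% |

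The loss is small for a test that is usually normal at baseline and nearly complete for one that is usually abnormal.

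**4. What the remaining rules do**

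Unscheduled values are left out, the first of repeated post-dose values is taken, and no worst post-baseline category is planned for laboratory tests. A transient extreme value can therefore be missed even in a patient who starts within range.

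**The case against.** The case on the other side has real force.

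- **Many tests are covered elsewhere.** Creatinine, BUN/urea, sodium, CRP and the liver tests keep values and changes as efficacy outputs. Peak creatinine and BUN are also summarised, and the Day 7 creatinine change is modelled. A reader might infer that the SAP drops laboratory values across the board. It does not, and protocol 7.7.3 promised the tables only for tests outside the efficacy analysis. This stands, and the point is limited to the 16 tests. The efficacy tables are still not a full substitute where they exist, because they use the ITT Combined Set. That set excludes patients recruited to unselected doses during the interim. With the protocol's estimate of 50 such recruits at 1:1:1:1, that is 50 × 2/4 = 25 patients.
- **Worsening has other routes.** Protocol 6.5 requires abnormal results judged clinically significant, including worsening from baseline, to be recorded as adverse events. Those events are tabulated by arm, and every value is listed by patient. The SOFA coagulation component partly covers thrombocytes. A reader might infer that worsening cannot be seen at all, and that is not supported. However, the adverse event route depends on investigator judgment, and listings give no by-arm summary.
- **Dose selection.** A reader might infer that the choice of dose was, or could still be, affected. SAP 8.1.4 describes the interim analysis as already done, so a change to 9.2 cannot alter it. The DMC also had adverse event, death and laboratory outputs and could request more. Two of its tables are titled as laboratory results and are separate from the shift tables. Their layouts are not in the documents.
- **The text is not airtight.** SAP 9.2 speaks of summarising assessments by visit, and the general display rule in SAP Section 4 gives descriptive statistics for continuous variables. By-visit values could be read into that. Change from baseline for these tests could not, and the change history points towards shift tables.
- **Range tables are a defensible choice** when local laboratories report in different units. That explains the choice, but it does not remove the loss of information.
- **Entry criteria do not fix the baseline rates.** White cell count is one of four SIRS criteria, of which two are needed, and it may be low or high. The signs need not be present together at randomisation, and kidney injury may be diagnosed on urine output alone. This stands, so no particular baseline share is claimed.

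**Conclusion.** The point holds for 16 of the 20 tests in SAP 9.2.1 and 9.2.2. For these, the SAP does not name the change-from-baseline summary that protocol 7.7.3 plans and, on its plainest reading, does not name summaries of values either. Section 12 does not declare the departure. It was not hidden, since the change history states it.

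The consequence is certain in kind: a by-arm table with three categories cannot show further movement past a limit already crossed. Its size is not known. The percentages in the working rest on assumed distributions and show only how the loss grows with the share of patients abnormal at baseline. The pH example rests on nothing but the SAP's own range.

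This is a gap in the by-arm laboratory tables. It does not mean that laboratory harm would go undetected, and it gives no ground to question the dose already selected.

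**What to change.** In SAP 9.2:

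1. Add, for the Safety Set, by-visit descriptive statistics of values and change from baseline by treatment group for at least the 16 tests.
2. Replace the no-conversion rule for these tables by converting local results to standard units. Table 4-2 already does this for creatinine and CRP.
3. Add a worst post-baseline table that includes unscheduled values, using the lowest value, the highest value or both, as relevant to each test. Upper-limit multiples or fold-rises alone would not do, because they cannot show falls in haemoglobin, thrombocytes, albumin, bicarbonate or pH.
4. Keep the shift tables as the supplement that the protocol describes.

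In SAP Section 12, list the change to the laboratory analyses.

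The data are already collected. The cost is unit standardisation, programming and more tables. The benefit is to the final safety report and any DMC safety review still outstanding.

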Efficacy endpoints will be summarized for all four treatment groups excluding patients recruited whilst the interim analysis is performed to treatment arms not selected for Part 2. Any analyses of the other efficacy endpoints will compare the optimal recAP dose and placebo treatment groups only. All safety data will be summarized for all four treatment

groups including patients recruited at any point in the study. Similarly, all data listings will include patients recruited at any point in the study.

See also [Section 4.3](#) for definitions of the analysis sets used in the study, which also state which patients (i.e. recruited during Part 1, or recruited during Part 2) are included in each analysis set.

Display of data

Continuous variables will be summarized using descriptive statistics, including but not limited to the mean, standard deviation, median, lower quartile, upper quartile, minimum value, and maximum value. For the summary statistics of all numerical variables minimum and maximum will be displayed to the same level of precision as reported, unless otherwise specified. Mean, median, lower quartile and upper quartile will be displayed to one level of precision greater than the data collected. Standard deviation / standard error will be displayed to two levels of precision greater than the data collected. P-values will be rounded to three decimal places. If a p-value is less than 0.001 it will be reported as “<0.001.” If a p-value is greater than 0.999 it will be reported as “>0.999”.

Categorical variables will be summarized using frequency counts and percentages. When count data are presented, the percentage will be suppressed if the count is zero in order to draw attention to the non-zero counts. The denominator for all percentages will be the number of patients in that treatment within the analysis set of interest, unless otherwise specified. All percentages will be presented to one decimal place. Categorical summaries will display all categories available on the electronic case report form (eCRF). A row denoted “Missing” will be included in count tabulations only when information is missing for a categorical variable.

All data summaries will be provided by treatment arm.

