9.2.2. Clinical Chemistry

The following laboratory tests will be included: arterial pH, CRP, urea, creatinine, creatine phosphokinase, total protein, albumin, glucose, sodium, potassium, chloride, bicarbonate, and lactate. All chemistry data by patient will be presented in a listing.

The following normal range will be used for arterial pH: 7.35 – 7.45

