9.5. Electrocardiogram

All patients will have a 12-lead ECG performed at baseline, Day 3, and Day 14.

Summary tables presenting observed values and changes from baseline will be presented for ventricular rate (bpm), PR Interval (msec), QRS Duration (msec), QT Interval (msec), QTcB Interval (msec), by treatment group for patients in the Safety Set. Changes from baseline to each scheduled post-baseline visit will be presented.

The ECG interpretations will be summarized in shift tables comparing the ECG values of each post-baseline visit with the value at the baseline visit for the Safety Set. The percentage will be based on the number of patients who have attended the visit. In addition the worst post-baseline ECG value will be compared with the value at the baseline visit (with worst of all being Abnormal and best being Normal).

Electrocardiogram data for all patients will be presented in a listing.

10. Pharmacokinetics and Pharmacodynamics

The pharmacokinetics and pharmacodynamics analyses will be described in the Population Pharmacokinetics/ Pharmacodynamics Report Analysis Plan.

11. Interim Analysis

An unblinded interim analysis will be conducted on the Part 1 data to determine the optimal recAP dose for Part 2. This analysis will compare the 4 treatment groups from Part 1 on the primary efficacy endpoint, and a selection of the safety data. The interim analysis will be conducted when the first 7 days of laboratory data have been collected for 120 patients from Part 1, unless the patient was randomized but died or discontinued prior to completing 7 days.

To maintain the blind, the interim analysis will be conducted and delivered by an unblinded PPD Biostatistics team located at a different site to the blinded PPD biostatistics personnel involved in the study. The results will be reviewed by an independent DMC, who will make the dose selection decision. A futility analysis will also be conducted at the interim analysis. If none of the 3 recAP doses in Part 1 show evidence of efficacy (i.e., all 3 groups have 1-sided, unadjusted p-value greater than 0.8), then the study will be terminated.

The following outputs will be produced for the Interim Analysis:

Table 14.1.1.1.1	Disposition at Interim Analysis All Enrolled Set
Table 14.1.1.6.1	Concomitant Medications at Interim Analysis Safety Set
Table 14.2.1.1.1	Summary of Time-Corrected Endogenous Creatinine Clearance at Interim Analysis ITT Combined Set

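### Laboratory abnormality percentages are taken over patients who attended the visit rather than patients tested, and no laboratory safety table shows the worst post-baseline value

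*SAP*

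**What the plan says.** SAP Section 9.2 plans by-visit shift and count tables against the local laboratory's normal ranges. Hematology and clinical chemistry "will be assessed at Baseline, Day 1, 3, 5, 7, 14, 21 and 28". Three rules govern what enters them:

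- **Which assessments:** "Only scheduled assessments will be included in the laboratory summaries".
- **Repeats:** "In case of repeat values the last assessment will be used for pre-dose visits and the first value for post-dose visits".
- **Denominator:** "The percentage will be based on the number of patients who have attended the visit". This overrides the general rule in SAP Section 4 (Display of data): "The denominator for all percentages will be the number of patients in that treatment within the analysis set of interest, unless otherwise specified".

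Section 9.2.2 sets the chemistry list: "The following laboratory tests will be included: arterial pH, CRP, urea" and ten further tests. Sections 9.2.1 and 9.2.2 also promise patient listings of all hematology and chemistry data. Nothing in Section 9.2 summarizes a patient's worst value after baseline. Section 9.5 does so for ECG: "In addition the worst post-baseline ECG value will be compared with the value at the baseline visit".

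**The concern.** The two points are separate.

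**Denominator.** A patient who attends but has no result for a test cannot be counted as abnormal, yet adds to the denominator. The printed percentage is then below the rate among those tested. If the share of untested attenders differs by arm, equal abnormality rates print as unequal ones.

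**Coverage.** In intensive care, tests outside the schedule are often ordered because something has changed. Those results are left out of the laboratory tables, and no table collects the most extreme value a patient reached. Safety and tolerability are a secondary objective, and these tables are the planned comparison of laboratory safety between arms.

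**Working it through.** The plan states no figure on this point, so there is none to reproduce.

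**1. Effect of the denominator.** Let p be the abnormality rate among patients tested at a visit and u the share of attenders with no result. Then

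printed rate = p × (tested / attended) = p × (1 − u).

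Neither p nor u is in the documents. The values below are assumptions.

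| p among tested | u = 0% | 2% | 5% | 10% | 20% |
|---|---|---|---|---|---|
| 10% | 10.0% | 9.8% | 9.5% | 9.0% | 8.0% |
| 20% | 20.0% | 19.6% | 19.0% | 18.0% | 16.0% |
| 40% | 40.0% | 39.2% | 38.0% | 36.0% | 32.0% |

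The relative shortfall is u itself: none if everyone is tested, one tenth if 10% are not.

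With p = 20% in both arms and u = 5% versus 15%, the table prints 0.20 × 0.95 = 19% and 0.20 × 0.85 = 17%. That is a 2-point difference with no difference among those tested. With u = 5% in both arms, both print 19%.

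**2. Where untested attenders are likely.** The hematology and chemistry panels are scheduled for every patient at the tabulated visits (protocol Section 6.3.7 and Table 13-1), so u may be small for most tests. Arterial pH differs. SAP Section 9.2.2 tabulates it and gives it a normal range, but it is in neither the protocol Section 6.3.7 list nor the panels of protocol Table 13-1 and SAP Table 15-1. The blood-gas item in those schedules is arterial oxygen pressure, and only for mechanically ventilated patients in the ICU or intermediate care unit.

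**3. Shift tables.** A shift needs a baseline and a visit value. The attendance rule also counts attenders who lack either one.

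**4. Coverage of the scheduled-only rule.** The tabulated post-baseline days are 1, 3, 5, 7, 14, 21 and 28, which is 7 of 28. The untabulated days between them number 1, 1 and 1 up to Day 7, then 6, 6 and 6, for a total of 3 + 18 = 21. Unscheduled results are therefore most exposed to omission after Day 7.

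**5. What else would tabulate such a result.**

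- Protocol Section 6.5 requires abnormal results that the investigator judges clinically significant to be recorded as adverse events, and SAP Section 9.1.1 tabulates those that are treatment-emergent.
- SAP Section 8.2.2.1 summarizes peak serum creatinine and peak blood urea nitrogen for Days 1 to 7.
- The same section tabulates reasons for starting renal replacement therapy. In protocol Section 6.3.9 the starting criteria include potassium, pH, urea and creatinine thresholds.

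An unscheduled abnormality outside these routes is listed if it is in the database, but no table compares it between arms.

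**The case against.** The case for leaving Section 9.2 alone is substantial.

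- **Other routes exist.** A reader might infer that abnormal results between visits are never tabulated. The documents do not support that, because the adverse event, peak-value and dialysis summaries above can each carry them. What is lost is narrower: unscheduled abnormalities that none of these catches.
- **Deaths.** A reader might infer that a patient who dies between visits adds nothing. In fact every scheduled result before death is tabulated, deaths up to the Day 28 visit are reported as serious adverse events, and cause of death is summarized (SAP Section 9.1.6). A patient who died before a visit is not in that visit's denominator.
- **Dilution is conditional.** It vanishes if every attender is tested. A missing-data row "will be included in count tabulations only when information is missing for a categorical variable", so the count tables would reveal the gap.
- **The first-value rule has no fixed direction.** If a repeat is ordered because the first value was abnormal, the abnormal value is kept. Only a later, worse repeat is lost.
- **The ECG rule is a limited precedent.** Section 9.5 does not say that unscheduled tracings count, and its shift tables use the same attendance denominator.
- **Scheduled-only tables have a merit.** They compare arms at common times. A worst-ever table depends on how often each patient is tested.

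All of this stands, and it limits the point without removing it. A missing-data row reveals untested patients but leaves the printed percentages unchanged, and it is specified for count tabulations only. Adverse event reporting depends on an investigator's judgment in patients whose laboratory values are often abnormal already. A listing does not compare arms. The dependence on testing frequency is a reason to present a worst-value table with care, beside the scheduled-only tables.

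**Conclusion.** The point holds in a limited form. The attendance denominator understates the rate among tested patients by exactly the fraction of attenders without a result. On the assumed range of 0% to 20%, a true 20% prints as 20% down to 16%, and unequal testing of 5% versus 15% separates equal rates by 2 points. The actual fraction is unknown. It may be near zero for the scheduled panels and is most likely to matter for arterial pH.

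Separately, Section 9.2 has no worst post-baseline summary and excludes unscheduled values, so some abnormalities reach no comparative table. The documents do not allow their number to be estimated.

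The consequence is confined to the laboratory safety tables; no efficacy analysis is affected. The current SAP (version 3.1) describes the interim analysis as already done (Section 8.1.4), so a change would serve the remaining outputs, chiefly the final tables.

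**What to change.** Two changes to SAP Section 9.2:

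1. **Denominator.** In the by-visit count tables, base percentages on patients with a result for that test. In the shift tables, base them on patients with both a baseline and a visit result. Print that n in each table.
2. **Worst value.** For each test, add a supplementary shift table from baseline to the lowest and, separately, to the highest post-baseline value through Day 28. Use the scheduled, unscheduled and repeat values held in the database, and keep the scheduled-only tables beside it.

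The cost is SAP wording, programming and extra tables, with no new data collection. The second change can use only what was entered, and protocol Section 6.3.7 does not say that unscheduled local results must be recorded. Its main drawback is that patients tested more often have more chances of an extreme value, and testing frequency may differ by arm. Show the number of tests per patient by arm, or a worst-value version restricted to scheduled visits, next to it.
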